6.2.1 APPENDIX 2.1: PHYSICIAN SURVEYS

Physician Prognostication Questions

1. For the type of transplant that has been chosen for your subject, what do you estimate survival at 1 year will be?

- Very good (more than 90%)
- Good (75-90%)
- Better than 50/50 (50-74%)
- Worse than 50/50 (25-49%)
- Bad (10-24%)
- Very bad (less than 10%)

2. Do you believe an individualized risk assessment tool that predicts 1 year non-relapse mortality based on the subjects' health and fitness would help you to make a recommendation to this subject about pursuing transplant?"

- Yes, better predicting 1 year non-relapse mortality would help
- Yes, but only if the tool also predicts overall survival
- No
- Unknown/don't want to answer

Physician Question for Subject Not Pursuing Transplantation after Enrollment

If subject does not proceed to HCT, please specify reason:

- Disease progression or relapse
- Insurance or economical barriers
- Patient is found to be too frail or too medically infirm per clinical team assessment
- Patient was found to have psychiatric or compliance issues per clinical team assessment
- Patient and/or family do not want the transplant any more
- Patient was found to be ineligible for the study based on information from research-driven tools included in this study
- Other, Specify:

6.3 APPENDIX 3: ASSESSMENT GUIDES AND INSTRUCTION

6.3.1 APPENDIX 3.1: FRAILTY PHENOTYPE GUIDE

Frailty will be ascertained by Physical Frailty Phenotype, which includes the measurement of 5 core criteria: weight loss, walking speed, grip strength, exhaustion, and physical activity. These measures reflect the concept that frailty is a syndrome with multiple criteria needing to be present to constitute being frail. Participants with 3, 4, or 5 components present are determined to be frail. Participants who meet 1 or 2 criteria are pre-frail. Those with none of the 5 components present are non-frail. This frailty assessment instrument consists of the following 5 measures:

- 1) **Measured Grip Strength:** Participant attempts to squeeze the dynamometer maximally 3 times with the dominant hand. Measured by a JAMAR hand dynamometer; use maximal score. Meets frailty criterion for grip strength for men if: ≤ 29 kg for BMI ≤ 24 or ≤ 30 kg for BMI 24.1–26 or ≤ 30 kg for BMI 26.1–28 or ≤ 32 kg for BMI > 28 . Meets frailty criterion for grip strength for women if: ≤ 17 kg for BMI ≤ 23 or ≤ 17.3 kg for BMI 23.1–26 or ≤ 18 kg for BMI 26.1–29 or ≤ 21 kg for BMI > 29 .
- 2) **Timed Walking Speed:** Participant will walk 4-meter length twice at his or her usual pace. Use average of 2 trials. Meets frailty criterion for slow walking speed for men if: $\leq .65$ m/s for height ≤ 173 cm (68 inches) or $\leq .76$ m/s for height > 173 cm (68 inches). Meets frailty criterion for slow walking speed for women if: $\leq .65$ m/s for height ≤ 159 cm (63 inches) or $\leq .76$ m/s for height > 159 cm (63 inches)
- 3) **Weight loss:** Meets criterion if: Lost $> 5\%$ body weight unintentionally in last year, or BMI < 18.5 kg/m²
- 4) **Exhaustion** is assessed using three self-reported items. Meets frailty criterion for exhaustion if answer: Felt unusually tired or unusually weak ‘all of the time’ or ‘most of the time’ or reported energy level was ≤ 3 , from the CES-D Depression Scale. The specific items to be read are:
 1. a. “In the past month, on the average, have you been feeling unusually tired during the day?”
 - Yes or
 - No or
 - Refused or Don’t Know.
 1. b. “If yes, have you been feeling unusually tired:”
 - All of the time or
 - Most of the time or
 - Some of the time or
 - Refused / Don’t Know.
 2. a. “In the past month, on the average, have you felt unusually weak?”
 - Yes or No or Refused or Don’t Know
 2. b. “If yes, have you been feeling weak:”
 - All of the time or
 - Most of the time or

- Some of the time or
 - Refused / Don't Know.
3. "Please rate your usual energy level on a scale from 0 to 10 where 0 is no energy and 10 is the most energy that you have ever had. Please give a number between 0 and 10 that describes your usual energy level while awake in the last month?" Record value between 0 and 10.
- 5) Physical Activity is assessed using six self-reported questions from the modified Minnesota Leisure Time Activities Questionnaire related to the amount of activities (and the corresponding task-specific MET intensity scores) that a person performed in a past two weeks. Meets frailty criterion for low activity for men if: <128 kcal of physical expenditure on activity scale per two-week period. Meets frailty criterion for low activity for women if: <90 kcal of physical expenditure on activity scale per two-week period. The MET scores per activity are: walking (w = 3.5), strenuous household chores (w = 4.5), strenuous outdoor chores (w = 4.5), dancing (w = 5.5), bowling (w = 3.0), and exercise (w = 4.5). To compute Kilocalories (kcal) expended per two-week period, use the formula: $\text{Kcal}/\text{period} = w * \text{Frequency (\# of sessions in 2 weeks)} * \text{Duration per session (minutes)} * \text{Body Weight (kg)}/60$.

6.3.2 APPENDIX 3.2: MONTREAL COGNITIVE ASSESSMENT (MoCA) GUIDE

Administration and Scoring Instructions

The Montreal Cognitive Assessment (MoCA) was designed as a rapid screening instrument for mild cognitive dysfunction. It assesses different cognitive domains: attention and concentration, executive functions, memory, language, visuoconstructional skills, conceptual thinking, calculations, and orientation. Time to administer the MoCA is approximately 10 minutes. The total possible score is 30 points; a score of 26 or above is considered normal.

Alternating Trail Making:

Administration: The examiner instructs the subject: *"Please draw a line, going from a number to a letter in ascending order. Begin here [point to (1)] and draw a line from 1 then to A then to 2 and so on. End here [point to (E)]."*

Scoring: Allocate one point if the subject successfully draws the following pattern:

1 – A – 2 – B – 3 – C – 4 – D – 5 – E, without drawing any lines that cross. Any error that is not immediately self-corrected earns a score of 0.

Visuoconstructional Skills (Cube):

Administration: The examiner gives the following instructions, pointing to the cube: *"Copy this drawing as accurately as you can, in the space below".*

Scoring: One point is allocated for a correctly executed drawing.

Drawing must be three-dimensional

All lines are drawn

No line is added

Lines are relatively parallel and their length is similar (rectangular prisms are accepted). A point is not assigned if any of the above-criteria are not met.

Visuoconstructional Skills (Clock):

Administration: Indicate the right third of the space and give the following instructions: *"Draw a clock. Put in all the numbers and set the time to 10 past 11".*

Scoring: One point is allocated for each of the following three criteria:

Contour (1 pt.): the clock face must be a circle with only minor distortion acceptable (e.g., slight imperfection on closing the circle);

Numbers (1 pt.): all clock numbers must be present with no additional numbers; numbers must be in the correct order and placed in the approximate quadrants on the clock face; Roman numerals are acceptable; numbers can be placed outside the circle contour;

Hands (1 pt.): there must be two hands jointly indicating the correct time; the hour hand must be clearly shorter than the minute hand; hands must be centered within the clock face with their junction close to the clock center.

A point is not assigned for a given element if any of the above-criteria are not met.

Naming:

Administration: Beginning on the left, point to each figure and say: *"Tell me the name of this animal"*.

Scoring: One point each is given for the following responses: (1) lion (2) rhinoceros or rhino (3) camel or dromedary.

Memory:

Administration: The examiner reads a list of 5 words at a rate of one per second, giving the following instructions: *"This is a memory test. I am going to read a list of words that you will have to remember now and later on. Listen carefully. When I am through, tell me as many words as you can remember. It doesn't matter in what order you say them"*. Mark a check in the allocated space for each word the subject produces on this first trial. When the subject indicates that (s)he has finished (has recalled all words), or can recall no more words, read the list a second time with the following instructions: *"I am going to read the same list for a second time. Try to remember and tell me as many words as you can, including words you said the first time."* Put a check in the allocated space for each word the subject recalls after the second trial.

At the end of the second trial, inform the subject that (s)he will be asked to recall these words again by saying, *"I will ask you to recall those words again at the end of the test."*

Scoring: No points are given for Trials One and Two.

Attention:

Forward Digit Span: Administration: Give the following instruction: *"I am going to say some numbers and when I am through, repeat them to me exactly as I said them"*. Read the five number sequence at a rate of one digit per second.

Backward Digit Span: Administration: Give the following instruction: "*Now I am going to say some more numbers, but when I am through you must repeat them to me in the backwards order.*" Read the three number sequence at a rate of one digit per second.

Scoring: Allocate one point for each sequence correctly repeated, (*N.B.:* the correct response for the backwards trial is 2-4-7).

Vigilance: Administration: The examiner reads the list of letters at a rate of one per second, after giving the following instruction: "*I am going to read a sequence of letters. Every time I say the letter A, tap your hand once. If I say a different letter, do not tap your hand*".

Scoring: Give one point if there is zero to one error (an error is a tap on a wrong letter or a failure to tap on letter A).

Serial 7s: Administration: The examiner gives the following instruction: "*Now, I will ask you to count by subtracting seven from 100, and then, keep subtracting seven from your answer until I tell you to stop.*" Give this instruction twice if necessary.

Scoring: This item is scored out of 3 points. Give no (0) points for no correct subtractions, 1 point for one correction subtraction, 2 points for two-to-three correct subtractions, and 3 points if the participant successfully makes four or five correct subtractions. Count each correct subtraction of 7 beginning at 100. Each subtraction is evaluated independently; that is, if the participant responds with an incorrect number but continues to correctly subtract 7 from it, give a point for each correct subtraction. For example, a participant may respond "92 - 85 - 78 - 71 - 64" where the "92" is incorrect, but all subsequent numbers are subtracted correctly. This is one error and the item would be given a score of 3.

Sentence repetition:

Administration: The examiner gives the following instructions: "*I am going to read you a sentence. Repeat it after me, exactly as I say it [pause]: I only know that John is the one to help today.*" Following the response, say: "*Now I am going to read you another sentence. Repeat it after me, exactly as I say it [pause]: The cat always hid under the couch when dogs were in the room.*"

Scoring: Allocate 1 point for each sentence correctly repeated. Repetition must be exact. Be alert for errors that are omissions (e.g., omitting "only", "always") and substitutions/additions (e.g., "John is the one who helped today;" substituting "hides" for "hid", altering plurals, etc.).

Verbal fluency:

Administration: The examiner gives the following instruction: *"Tell me as many words as you can think of that begin with a certain letter of the alphabet that I will tell you in a moment. You can say any kind of word you want, except for proper nouns (like Bob or Boston), numbers, or words that begin with the same sound but have a different suffix, for example, love, lover, loving. I will tell you to stop after one minute. Are you ready? [Pause] Now, tell me as many words as you can think of that begin with the letter F. [time for 60 sec]. Stop."*

Scoring: Allocate one point if the subject generates 11 words or more in 60 sec. Record the subject's response in the bottom or side margins.

Abstraction:

Administration: The examiner asks the subject to explain what each pair of words has in common, starting with the example: *"Tell me how an orange and a banana are alike"*. If the subject answers in a concrete manner, then say only one additional time: *"Tell me another way in which those items are alike"*. If the subject does not give the appropriate response (*fruit*), say, *"Yes, and they are also both fruit."* Do not give any additional instructions or clarification. After the practice trial, say: *"Now, tell me how a train and a bicycle are alike"*. Following the response, administer the second trial, saying: *"Now tell me how a ruler and a watch are alike"*. Do not give any additional instructions or prompts.

Scoring: Only the last two item pairs are scored. Give 1 point to each item pair correctly answered. The following responses are acceptable:

Train-bicycle = means of transportation, means of travelling, you take trips in both; Ruler-watch = measuring instruments, used to measure.

The following responses are not acceptable: Train-bicycle = they have wheels; Ruler- watch = they have numbers.

Delayed recall:

Administration: The examiner gives the following instruction: *"I read some words to you earlier, which I asked you to remember. Tell me as many of those words as you can remember."* Make a check mark (--) for each of the words correctly recalled spontaneously without any cues, in the allocated space.

Scoring: Allocate 1 point for each word recalled freely without any cues.

Optional:

Following the delayed free recall trial, prompt the subject with the semantic category cue provided below for any word not recalled. Make a check mark (--) in the allocated space if the subject remembered the word with the help of a category or multiple-choice cue. Prompt all non-recalled words in this manner. If the subject does not recall the word after the category cue, give him/her a multiple choice trial, using the following example instruction, "*Which of the following words do you think it was, NOSE, FACE, or HAND?*"

Use the following category and/or multiple-choice cues for each word, when appropriate:

| | | |
|---------|--|---|
| FACE: | category cue : part of the body | multiple choice : nose, face, hand multiple |
| VELVET: | category cue : type of fabric | choice : denim, cotton, velvet multiple |
| CHURCH: | category cue : type of building | choice : church, school, hospital multiple |
| OASIS: | category cue : type of flower | choice : rose, daisy, tulip multiple choice : |
| REO: | category cue : a colour | red, blue, green |

Scoring: No points are allocated for words recalled with a cue. A cue is used for clinical information purposes only and can give the test interpreter additional information about the type of memory disorder. For memory deficits due to retrieval failures, performance can be improved with a cue. For memory deficits due to encoding failures, performance does not improve with a cue.

Orientation:

Administration: The examiner gives the following instructions: "Tell me the date today". If the subject does not give a complete answer, then prompt accordingly by saying: "*Tell me the [year, month, exact date, and day of the week].*" Then say: "*Now, tell me the name of this place, and which city it is in.*"

Scoring: Give one point for each item correctly answered. The subject must tell the exact date and the exact place (name of hospital, clinic, and office). No points are allocated if subject makes an error of one day for the day and date.

TOTAL SCORE: Sum all sub scores listed on the right-hand side. Add one point for an individual who has 12 years or fewer of formal education, for a possible maximum of 30 points. A final total score of 26 and above is considered normal.

MoCA Version August 18, 2010

6.3.3 APPENDIX 3.3: REMOTE ADMINISTRATION OF FOLLOW-UP ASSESSMENTS

This study includes three assessments typically performed in-person at routine visits (Table 1). In-person testing at the time of a routine visit remains the preferred method of testing. However, when not feasible because the subject and/or research team will not be on site, the 4-meter walk and MoCA cognitive assessment can be performed remotely following previously validated methods in small non-HCT populations. Grip strength requires a dynamometer device and thus is not feasible to administer remotely. A protocol deviation will be reported for subjects who are unable to complete this assessment.

| Assessment | Timepoints | Proposed Change |
|--|----------------------------|--|
| Montreal Cognitive Assessment (MoCA) for cognition | Baseline, D100 | Site staff will administer MoCA by audio-visual teleconference. If AV conference is not available, a modified telephone version may be administered. |
| Frailty phenotype - Walk Speed, 4-meter | Baseline, D100, D180, D365 | Site staff will administer 4-meter walk test by audio-visual teleconference. If AV conference is not available, the subject may self-report results of the walk test by telephone. |
| Frailty phenotype- Grip Strength | Baseline, D100, D180, D365 | This assessment will be omitted from remote visits. |

6.3.3.1 Remote Montreal Cognitive Assessment (MoCA)

Using audio-visual teleconference, the MOCA can be performed as a virtual bedside test with same elements and score. This follows instructions from the developer (<https://www.mocatest.org/remote-moca-testing/>). Although preferred as this most likely recapitulates the validity and reliability of an in-person test, a telephone cognitive assessment is an acceptable alternative. Several elements of the MoCA require audio-visual interpretation (trail making, cube, clock, animal naming). However, the remaining elements can be administered by telephone for a total of 22 points (compared to 30 points for the in-person and audio-visual teleconference methods). In one study evaluating the correlation of MoCA and telephone MoCA (i.e., T-MoCA) among patients having a prior transient ischemic attack or stroke in 91 patients, the authors found acceptable reliability for cognitive impairment when considering all domains.⁷⁴ Although data are not available for Spanish or Mandarin versions of T-MoCA, the tool used in the primary assessment at baseline (English, Spanish or Mandarin) would be used. Alternative cognitive tools exist (e.g., the 5 minute MoCA) yet employ different questions and thus results cannot be directly compared.^{75,76}

MoCA Full Audio-Visual Conference Administration

The rater proceeds as follows.

1. Identify yourself, from which clinic/institution you are from and in which city you are located.
2. Tell the subject the purpose of your call, obtain their verbal consent to proceed.

3. Instruct the subject to get a white sheet of paper, a pencil and an eraser, and to isolate themselves in a quiet room.
4. Show the subject the visual section of the MoCA
 - 1 **Trails:** Show the subject the Trail and say: "Please **tell me** where the arrow should go next to repeat the pattern I am showing you."
 - 2 **Cube:** Show them the cube and say: "Copy the cube"
 - 3 **Clock:** "Draw a clock. Put in all the numbers and set the time to 10 past 11"
 - 4 **Animal naming:** "Tell me the name of these animals"
5. The rest of the test is done the same way as in the clinic except for the Orientation:
 - 5 **Date:** "Look straight at the camera and tell me today's date, day of the week, month and year"
 - 6 **Place:** "From what Clinic/Institution am I calling you from?"
 - 7 **City:** "What is the city in which our clinic/institution is located?"

Telephone MoCA (MoCA-Blind) Administration

The Montreal Cognitive Assessment (MoCA)- BLIND is an adapted version of the original MoCA, a rapid screening instrument for mild cognitive dysfunction. The MoCA-BLIND assesses different cognitive domains: attention and concentration, memory, language, conceptual thinking, calculations, and orientation. It contains the same items as the original MoCA except those requiring visual abilities have been removed. Time to administer the MoCA- BLIND is approximately 5-10 minutes. The total possible score is 22 points; a score of 18 or above is considered normal. This cutoff score is suggestive as it has not been validated thus far.

1-Memory:

Administration: The examiner reads a list of 5 words at a rate of one per second, giving the following instructions: "*This is a memory test. I am going to read a list of words that you will have to remember now and later on. Listen carefully. When I am through, tell me as many words as you can remember. It doesn't matter in what order you say them*". Mark a check in the allocated space for each word the subject produces on this first trial. When the subject indicates that (s)he has finished (has recalled all words), or can recall no more words, read the list a second time with the following instructions: "*I am going to read the same list for a second time. Try to remember and tell me as many words as you can, including words you said the first time.*" Put a check in the allocated space for each word the subject recalls after the second trial.

At the end of the second trial, inform the subject that (s)he will be asked to recall these words again by saying, "*I will ask you to recall those words again at the end of the test.*"

Scoring: No points are given for Trials One and Two.

2-Attention:

Forward Digit Span: Administration: Give the following instruction: "*I am going to say some numbers and when I am through, repeat them to me exactly as I said them*". Read the five number sequence at a rate of one digit per second.

Backward Digit Span: Administration: Give the following instruction: “*Now I am going to say some more numbers, but when I am through you must repeat them to me in the backwards order.*” Read the three number sequence at a rate of one digit per second.

Scoring: Allocate one point for each sequence correctly repeated, (*N.B.:* the correct response for the backwards trial is 2-4-7).

Vigilance: Administration: The examiner reads the list of letters at a rate of one per second, after giving the following instruction: “*I am going to read a sequence of letters. Every time I say the letter A, tap your hand once. If I say a different letter, do not tap your hand*”.

Scoring: Give one point if there is zero to one errors (an error is a tap on a wrong letter or a failure to tap on letter A).

Serial 7s: Administration: The examiner gives the following instruction: “*Now, I will ask you to count by subtracting seven from 100, and then, keep subtracting seven from your answer until I tell you to stop.*” Give this instruction twice if necessary.

Scoring: This item is scored out of 3 points. Give no (0) points for no correct subtractions, 1 point for one correction subtraction, 2 points for two-to-three correct subtractions, and 3 points if the participant successfully makes four or five correct subtractions. Count each correct subtraction of 7 beginning at 100. Each subtraction is evaluated independently; that is, if the participant responds with an incorrect number but continues to correctly subtract 7 from it, give a point for each correct subtraction. For example, a participant may respond “92 – 85 – 78 – 71 – 64” where the “92” is incorrect, but all subsequent numbers are subtracted correctly. This is one error and the item would be given a score of 3.

3-Sentence repetition:

Administration: The examiner gives the following instructions: “*I am going to read you a sentence. Repeat it after me, exactly as I say it [pause]: **I only know that John is the one to help today.***” Following the response, say: “*Now I am going to read you another sentence. Repeat it after me, exactly as I say it [pause]: **The cat always hid under the couch when dogs were in the room.***”

Scoring: Allocate 1 point for each sentence correctly repeated. Repetition must be exact. Be alert for errors that are omissions (e.g., omitting “only”, “always”) and substitutions/additions (e.g., “John is the one who helped today;” substituting “hides” for “hid”, altering plurals, etc.).

4-Verbal fluency:

Administration: The examiner gives the following instruction: “*Tell me as many words as you can think of that begin with a certain letter of the alphabet that I will tell you in a moment. You can say any kind of word you want, except for proper nouns (like Bob or Boston), numbers, or*

words that begin with the same sound but have a different suffix, for example, love, lover, loving. I will tell you to stop after one minute. Are you ready? [Pause] Now, tell me as many words as you can think of that begin with the letter F. [time for 60 sec]. Stop.

Scoring: Allocate one point if the subject generates 11 words or more in 60 sec. Record the subject's response in the bottom or side margins.

5-Abstraction:

Administration: The examiner asks the subject to explain what each pair of words has in common, starting with the example: *"Tell me how an orange and a banana are alike"*. If the subject answers in a concrete manner, then say only one additional time: *"Tell me another way in which those items are alike"*. If the subject does not give the appropriate response (*fruit*), say, *"Yes, and they are also both fruit."* Do not give any additional instructions or clarification. After the practice trial, say: *"Now, tell me how a train and a bicycle are alike"*. Following the response, administer the second trial, saying: *"Now tell me how a ruler and a watch are alike"*. Do not give any additional instructions or prompts.

Scoring: Only the last two item pairs are scored. Give 1 point to each item pair correctly answered. The following responses are acceptable:

Train-bicycle = means of transportation, means of travelling, you take trips
in both; Ruler-watch = measuring instruments, used to measure.

The following responses are **not** acceptable: Train-bicycle = they have wheels;
Ruler- watch = they have numbers.

6-Delayed recall:

Administration: The examiner gives the following instruction: *"I read some words to you earlier, which I asked you to remember. Tell me as many of those words as you can remember."* Make a check mark (√) for each of the words correctly recalled spontaneously without any cues, in the allocated space.

Scoring: Allocate 1 point for each word recalled freely without any cues.

Optional:

Following the delayed free recall trial, prompt the subject with the semantic category cue provided below for any word not recalled. Make a check mark (✓) in the allocated space if the subject remembered the word with the help of a category or multiple-choice cue. Prompt all non-recalled words in this manner. If the subject does not recall the word after the category cue, give him/her a multiple choice trial, using the following example instruction, “Which of the following words do you think it was, NOSE, FACE, or HAND?”

Use the following category and/or multiple-choice cues for each word, when appropriate:

| | | |
|---------|--|---|
| FACE: | category cue : part of the body | multiple choice : nose, face, hand |
| VELVET: | category cue : type of fabric | multiple choice : denim, cotton, velvet |
| CHURCH: | category cue : type of building | multiple choice : church, school, hospital |
| DAISY: | category cue : type of flower | multiple choice : rose, daisy, tulip |
| RED: | category cue : a colour | multiple choice : red, blue, green |

Scoring: No points are allocated for words recalled with a cue. A cue is used for clinical information purposes only and can give the test interpreter additional information about the type of memory disorder. For memory deficits due to retrieval failures, performance can be improved with a cue. For memory deficits due to encoding failures, performance does not improve with a cue.

7-Orientation:

Administration: The examiner gives the following instructions: “Tell me the date today”. If the subject does not give a complete answer, then prompt accordingly by saying: “Tell me the [year, month, exact date, and day of the week].” Then say: “Now, tell me the name of this place, and which city it is in.”

Scoring: Give one point for each item correctly answered. The subject must tell the exact date and the exact place (name of hospital, clinic, office). No points are allocated if subject makes an error of one day for the day and date.

TOTAL SCORE: Sum all subscores listed on the right-hand side. Add one point for an individual who has 12 years or fewer of formal education, for a possible maximum of 22 points. A final total score of 18 and above is considered normal.

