3.2.5 Development of cognitive decline

The MoCA will be performed at baseline and day 100. Cognitive decline will be defined as a 2 point or greater decline from baseline on the total score at the day 100 re-evaluation. Cognitive decline will be assessed in all patients in subgroups who do and who do not have relapse of their malignancy prior to day 100.

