| | 1st trial | | | | | | |
| | 2nd trial | | | | | | |
| ATTENTION | Read list of digits (1 digit/ sec.). | Subject has to repeat them in the forward order [] 2 1 8 5 4 | | | | | ___/2 |
| | | Subject has to repeat them in the backward order [] 7 4 2 | | | | | |
| | Read list of letters. The subject must tap with his hand at each letter A. No points if ≥ 2 errors | [] FBACMNAAJKLBAFAKDEAAAJAMOF AAB | | | | | ___/1 |
| | Serial 7 subtraction starting at 100 | [] 93 | [] 86 | [] 79 | [] 72 | [] 65 | ___/3 |
| | | 4 or 5 correct subtractions: 3 pts , 2 or 3 correct: 2 pts , 1 correct: 1 pt , 0 correct: 0 pt | | | | | |
| LANGUAGE | Repeat : I only know that John is the one to help today. [] | | | | | | ___/2 |
| | The cat always hid under the couch when dogs were in the room. [] | | | | | | |
| | Fluency / Name maximum number of words in one minute that begin with the letter F [] ____ (N ≥ 11 words) | | | | | | ___/1 |
| ABSTRACTION | Similarity between e.g. banana - orange = fruit [] train - bicycle [] watch - ruler | | | | | | ___/2 |
| DELAYED RECALL | Has to recall words WITH NO CUE | FACE [] | VELVET [] | CHURCH [] | DAISY [] | RED [] | Points for UNCUEDE recall only |
| | Category cue | | | | | | |
| Optional | Multiple choice cue | | | | | | |
| ORIENTATION | [] Date [] Month [] Year [] Day [] Place [] City | | | | | | ___/6 |
| © Z.Nasreddine MD | | www.mocatest.org | | Normal ≥ 26 / 30 | | TOTAL ___/30 | |
| Administered by: _____ | | Add 1 point if ≤ 12 yr edu | | | | | |

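### The telephone MoCA keeps a hand-tap item without asking for an audible tap, so up to 1 of its 22 points can depend on test mode

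*Protocol*

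**What the plan says.** Appendix 3.3 (section 6.3.3) prefers in-person testing, then video, and permits a telephone version of the MoCA where video is not available. Section 6.3.3.1 names four elements that need audio-visual contact (trail making, cube, clock and animal naming) and continues: "However, the remaining elements can be administered by telephone for a total of 22 points". In-person and video administration carry 30 points. The telephone form is the MoCA-Blind, described thus: "It contains the same items as the original MoCA except those requiring visual abilities have been removed".

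Vigilance is among the items kept. The subject is told: "Every time I say the letter A, tap your hand once. If I say a different letter, do not tap your hand". One point is given for zero or one error, where "an error is a tap on a wrong letter or a failure to tap on letter A". The instruction and scoring match the in-person guide in Appendix 3.2. The letter list is printed on the MoCA sheet in Appendix 2: "FBACMNAAJKLBAFAKDEAAAJAMOF AAB".

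Section 3.2.5 sets the endpoint: "Cognitive decline will be defined as a 2 point or greater decline from baseline on the total score", comparing day 100 with baseline. Section 5.8.5 builds a change score between the two visits and relates decline to CHARM risk group by logistic regression. Neither section says how scores from different modes are compared.

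**The concern.** The MoCA-Blind drops what the subject would have to see. By telephone the rater cannot see either, and the protocol's list of elements needing audio-visual contact does not cover that side. Vigilance is the only retained scored item answered by a gesture; every other one is answered in speech. The script does not ask for an audible tap, offers no spoken substitute and includes no check that taps reach the rater.

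An attentive subject whose taps are not heard is then either scored as failing or credited on trust. In both cases the point does not measure attention. It matters because the endpoint is a within-subject change with a threshold of only 2 points, and the foreseeable pairing is a baseline at which taps were seen followed by a telephone test at day 100.

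**Working it through.** **1. The telephone total.** Item points from section 6.3.3.1 and the MoCA sheet: digit span 2 + vigilance 1 + serial sevens 3 + sentence repetition 2 + fluency 1 + abstraction 2 + delayed recall 5 + orientation 6 = 22. This reproduces the protocol's figure. Adding the removed visuospatial/executive points (5) and naming points (3) gives 22 + 8 = 30, also as stated. The 22 is reached only with the vigilance point; without it the sum is 21.

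**2. What unheard taps do to the item.** The list has 29 letters, 11 of them A. If no tap is detected and the rule is applied literally, that is 11 errors. Two already lose the point, so the item scores 0. The loss is at most 1 point, and only for a subject who earned that point at baseline.

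**3. Against the threshold.** On the shared items, an otherwise stable subject moves by −1, short of −2. If the totals were instead rescaled in proportion, the point would be worth 30/22 = 1.36, still below 2. At least one further point must be lost before decline is recorded.

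**4. Which visits can differ in mode.** Table 4.2.4 attaches the remote-testing footnote to the MoCA at day 100 only, and Appendix 3.3 is titled for follow-up assessments. The table inside Appendix 3.3, however, lists both baseline and day 100. If both visits are by telephone and scored alike, the shift largely cancels.

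**5. Illustrative size once scores are on common items.** The documents give no SD for MoCA change, so it is assumed. Take a stable subject, a normal change score and a continuity-corrected cut at −1.5. The chance of being classed as declined is Φ(−1.5/SD) with no artefact and Φ((−1.5 + 1)/SD) = Φ(−0.5/SD) with one point lost to mode.

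| Assumed SD | No artefact | One point lost |
|---|---|---|
| 1.0 | 6.7% | 30.9% |
| 1.5 | 15.9% | 36.9% |
| 2.0 | 22.7% | 40.1% |
| 2.5 | 27.4% | 42.1% |
| 3.0 | 30.9% | 43.4% |

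These figures apply only to telephone-tested subjects whose taps go unheard and whose baseline was in another mode.

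**6. The same calculation on raw totals.** If a 22-point day-100 total were subtracted directly from a 30-point baseline, a stable subject with full marks on the removed items would fall by 8 points before vigilance is considered. The chance of being classed as declined is then Φ((−1.5 + 8)/SD), which runs from 98.5% at SD 3 to practically 100% at SD 1. The vigilance point can add at most about 1.5 percentage points.

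**The case against.** The strongest reply is that loss of the point is assumed, not shown. A tap makes a sound, a rater may hear it or ask for it to be louder, and the script does not forbid this. Sections 4.2.6 and 6.3.3.1 add support: staff who give cognitive tests must be trained, each site should have a certified MoCA super-user, and the protocol cites a 91-patient study reporting acceptable reliability by telephone. Telephone testing is the last resort, and cognitive decline is one of about ten secondary endpoints; the primary NRM endpoint is untouched.

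Most of this stands, and it limits the size of the point. It does not remove it. The protocol relies on standardized administration to reduce measurement error, and it adapts other tests to the mode: the video version rewords trail making and orientation, and grip strength is omitted remotely. Here it leaves each rater to decide what to do with an unheard tap.

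A reader might go further and infer that telephone-tested subjects will lose the point, or that 40% of stable ones will be counted as declining. The documents do not support either. They neither require nor rule out audible tapping, they do not give the share of telephone tests or of unheard taps, and the 40% depends on an assumed SD and on comparable totals.

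It could also be said that repairing the 22-versus-30 mismatch makes this point redundant. It does not, because vigilance is one of the shared items and would be carried into any common-item or rescaled comparison.

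**Conclusion.** The point holds as a limited defect in the telephone script. An item scored from hand taps has been carried over to a mode in which the rater cannot see them, with no adaptation. Its reach is at most 1 of 22 points, for subjects tested by telephone at day 100 after a baseline in person or by video, who earned the point at baseline and whose taps go unheard. The number of such subjects is unknown.

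The artefact cannot produce a decline on its own; it makes one more likely when combined with ordinary variation. The rise from 23% to 40% is an illustration under no true change, SD 2.0 and common-item scoring. It is not an estimate for this study. The larger issue in the same sections is the 8-point gap in maximum score, for which sections 3.2.5 and 5.8.5 give no conversion. The two are best corrected together.

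**What to change.** In the vigilance item of the telephone script, ask the subject to tap audibly on the table or handset at each letter A, and have the rater confirm before scoring that taps can be heard. Add the same line to rater training.

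In sections 3.2.5 and 5.8.5, state that for any subject tested by telephone at either visit, the day-100 change is computed only on items given in both modes, with vigilance left out at both visits where taps could not be heard. This also closes the 22-versus-30 gap.

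The cost is one sentence in Appendix 3.3 and one scoring rule. The downside is a slightly shorter score for these subjects: 22 shared points, or 21 where vigilance is dropped. An audible tap is preferable to a spoken reply because it keeps the response motor, as it is in clinic.
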